2.6 Procedure

Baseline assessments were conducted prior to randomization. Following baseline measurements, participants were randomly assigned to one of the three groups. Exercise

interventions were conducted over an 8-week period. Post-intervention assessments were performed using the same measurement tools as at baseline.

2.7 Ethical Considerations

The study was conducted in accordance with the Declaration of Helsinki and was approved by the Çukurova University Non-Interventional Clinical Research Ethics Committee (decision no: 127/64, dated November 4, 2022) and was conducted in accordance with the Declaration of Helsinki. Written informed consent was obtained from all parents or legal guardians before participation.

2.8 Statistical Analysis

A per-protocol analysis approach was used, and pre-test and post-test measurements were analyzed for all three groups. Statistical analyses were performed using SPSS software (IBM Corporation, Version 22, Armonk, NY, USA). One-way analysis of variance (ANOVA) and Pearson's chi-square test were used to analyze baseline demographic characteristics of the participants. To examine the primary outcome variables, a two-factor repeated measures analysis of variance (group \times time) with Bonferroni post hoc correction was applied. Within-group changes were analyzed using paired-samples t-tests. A p-value of less than 0.05 was considered statistically significant.

4. Results

Primary Outcomes

Cognitive Function

Cognitive function was assessed using the Stroop Test and the Visual-Auditory Digit Span Test. Changes from baseline to post-intervention scores were used to evaluate attention, executive functions, working memory, and cognitive processing speed. Both intervention groups demonstrated improvements in cognitive functions. The Gince Zumba group demonstrated greater gains in attention-related abilities, while the Square Stepping Exercise group showed more pronounced improvements in high-level cognitive functions."

Secondary Outcomes

Motor Performance

Motor performance was evaluated using the BlazePod Reaction Time Test. Changes in reaction time from baseline to post-intervention were analyzed. While both intervention groups exhibited significant improvements in motor performance relative to the control group, the enhancements were more pronounced in the Square Stepping Exercise group

Behavioral Symptoms

Behavioral outcomes were assessed using the Conners Parent Rating Scale. Changes in total and subscale scores from baseline to post-intervention were used to evaluate ADHD-related behavioral symptoms. Both intervention groups demonstrated significant reductions in ADHD-related behavioral symptoms relative to the control group and baseline measurements.

4. References

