Official Title

Effects of Structured Exercise Programs on Cognitive Function, Motor Skills, and Behavioral Outcomes in Children with Attention Deficit Hyperactivity Disorder

NCT Number: Pending

Document Type: Study Protocol

Date: November 4, 2022

1. Introduction

Attention Deficit Hyperactivity Disorder (ADHD) is one of the most common neurodevelopmental disorders in childhood and is characterized by symptoms of inattention, hyperactivity, and impulsivity. In addition to behavioral symptoms, children with ADHD frequently experience impairments in executive functions, attention control, working memory, and motor coordination.

Recent research suggests that structured physical exercise programs may positively influence cognitive and motor functions in children with ADHD. Exercise-based interventions are thought to enhance neurocognitive functioning through increased arousal, improved neural efficiency, and enhanced executive control processes. Among these interventions, rhythm-based and cognitively demanding exercises have gained increasing attention.

Gince Zumba is a movement-based exercise program that combines rhythmic movements, coordination, and aerobic activity, whereas Square Stepping Exercise (SSE) involves structured step patterns requiring visuospatial processing, motor planning, and executive control. Both exercise types may provide cognitive stimulation in addition to physical activity.

The aim of this study was to investigate the effects of Gince Zumba and Square Stepping exercises on motor and cognitive functions in children with ADHD.

2. Methods

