2.1 Study Design

This study was designed as a randomized controlled experimental trial with three parallel groups.

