2.4 Intervention Programs

Gince Zumba Group (GZG):

Participants in the Gince Zumba group participated in a structured exercise program for **8 weeks**, with **2 sessions per week**, each session lasting approximately **50 minutes**. The program included rhythmic movements, coordination tasks, and aerobic components appropriate for children.

Square Stepping Exercise Group (SSEG):

Participants in the Square Stepping Exercise group followed an **8-week SSE** program with **2 sessions per week**, each lasting **50 minutes**. The exercises involved progressively complex stepping patterns designed to challenge motor coordination and cognitive processing.

Control Group:

Participants in the control group did not participate in any regular physical activity program during the study period and continued their usual daily activities.

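### Per-protocol is the only analysis approach the protocol names for this randomised trial, so outcome-related removal that differs between arms can bias the contrasts involving those arms

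*Protocol*

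**What the plan says.** The Protocol describes a "randomized controlled experimental trial with three parallel groups" (section 2.1). Allocation came after the baseline tests and before the 8 weeks of exercise: "Following baseline measurements, participants were randomly assigned to one of the three groups" (section 2.6). The aim is "to investigate the effects of Gince Zumba and Square Stepping exercises on motor and cognitive functions" (Introduction).

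Section 2.8 gives the analysis approach: "A per-protocol analysis approach was used, and pre-test and post-test measurements were analyzed for all three groups". It names no other approach, and neither does any other section. The primary outcomes are then tested with a group-by-time repeated-measures ANOVA with Bonferroni correction at 0.05.

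The Results section compares the arms. On the primary cognitive outcome, "The Gince Zumba group demonstrated greater gains in attention-related abilities", while Square Stepping is credited with the larger improvement in higher-level functions. On motor performance both programmes are placed above control, and "the enhancements were more pronounced in the Square Stepping Exercise group". On behavioural symptoms both are placed above control.

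**The concern.** Randomisation makes the arms comparable as allocated. A per-protocol approach keeps or drops children according to what happened afterwards, so the arms compared need no longer be the arms randomised. Two conditions are needed for bias in a difference between two arms: removal must be related to outcome, and it must differ between those arms in rate or kind.

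The protocol gives reasons to expect that removals could differ:

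- **Exercise arms.** Each has 16 sessions to attend (8 weeks × 2 per week, section 2.4).
- **Control arm.** It has no sessions, but it must stay out of regular activity programmes (section 2.4). Taking up structured exercise during the study is also an exclusion criterion (section 2.2), and that can be seen only after allocation. Control children can therefore deviate too, in a different way.
- **Gince Zumba versus Square Stepping.** The schedules match but the content does not. For the first, "The program included rhythmic movements, coordination tasks, and aerobic components appropriate for children"; the second uses "progressively complex stepping patterns designed to challenge motor coordination and cognitive processing". The two programmes may lose different numbers or kinds of children.

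At stake are the between-group statements in Results, including the primary cognitive comparison of the two programmes.

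**Working it through.** **Inputs.** The protocol gives no sample size, SD, drop-out or number removed, so there is no figure to reproduce. Everything below is an illustration. The assumptions are a true effect of zero, 20 or 30 children per arm, removal of the least adherent, and a correlation r of 0.3 to 0.5 between adherence and change. Change is scored so that higher means more improvement, and bias is in SDs of change.

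**Bias formula.** If the least adherent fraction f is removed, the mean change of those kept shifts by r × h(f), where h(f) = φ(z_f)/(1 − f). This gives h(0.1) = 0.195, h(0.2) = 0.350 and h(0.3) = 0.497. The bias in a contrast is the difference between the shifts in its two arms.

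*Exercise versus control*

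| Removed, exercise / control | Calculation | Bias (SD) |
|---|---|---|
| 20% / 0% | r × 0.350 | 0.10–0.17 |
| 30% / 0% | r × 0.497 | 0.15–0.25 |
| 20% / 10% | r × (0.350 − 0.195) = r × 0.155 | 0.05–0.08 |
| 30% / 20% | r × (0.497 − 0.350) = r × 0.147 | 0.04–0.07 |
| equal, same kind | r × 0 | 0 |

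*Gince Zumba versus Square Stepping*

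| Removal | Calculation | Bias (SD) |
|---|---|---|
| 30% / 10% | r × (0.497 − 0.195) = r × 0.302 | 0.09–0.15 |
| 20–30% in both, related to change in one programme only | r × h(f) − 0 | 0.10–0.25 |

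**Type I error of the group-by-time test.** With two time points this test is a one-way ANOVA on change scores. It was simulated for three arms at nominal 5%.

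| Removed (two exercise arms / control) | Type I error |
|---|---|
| none | about 5% |
| 20% / 20% / 0% | about 6–9.5% |
| 30% / 30% / 0% | about 7–14% |
| 20% / 20% / 10%, same mechanism | about 5–6% |
| 30% / 30% / 20%, same mechanism | about 5–6% |
| 20% in all arms, same kind | about 5% |

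**Bonferroni-adjusted test of the two programmes** (no control removal). The false-positive rate is 1.6–1.7% with all children. It is about 2–3% with 30% and 10% removed. It is about 2–5% with equal removal related to change in one programme only.

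**When removal follows something other than change.** Let each score be a stable level plus independent error, with reliability 0.6 or 0.8. Remove 20–30% from an exercise arm only, with adherence correlated 0.5 with the driver.

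- *Driver is the stable level:* per-protocol bias is 0.00, because the level cancels in the change score.
- *Driver is the baseline score:* the correlation of baseline with change is −√((1 − reliability)/2), that is −0.316 or −0.447. The bias runs from 0.5 × −0.316 × 0.350 = −0.06 to 0.5 × −0.447 × 0.497 = −0.11, opposite in sign to the change-driven case.
- *Driver is change:* bias is 0.17–0.25, as in the first table.

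**The case against.** A reader might infer that any removal biases every contrast. That is not so. Removal from control alone cannot bias the difference in means between the two programmes, and removal from Gince Zumba alone cannot bias Square Stepping versus control. Equal removal of the same kind gives no bias. The point holds only for the arms in which removal differs.

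A reader might also infer a false-positive rate of up to 14%. That figure needs zero removal from control, and the protocol does not support assuming this because control children can deviate as well. With some control removal by the same mechanism, the rate falls to about 5–6%. A different mechanism in control could give more or less bias.

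A third tempting inference is that the reported results are biased, or biased in favour of exercise. The document reports no removals, so neither follows, and the bias can be nil or reversed. The inflation for the comparison of the two programmes is also modest unless removal is related to change in one programme and not in the other. Nothing beyond the differing content suggests that.

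Finally, the protocol does not call per-protocol its sole approach, and a SAP may add an as-randomised set. That stands as a limit on the claim. It does not remove the point, because the approach is a choice the protocol states, not a detail it leaves open. How the per-protocol set is defined may properly sit in a SAP and is not criticised here. Nor does the second half of the section 2.8 sentence settle the matter: it refers to all three groups, not to all randomised children.

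**Conclusion.** The concern holds in limited form. Naming only a per-protocol approach gives up the protection of randomisation for any contrast whose arms lose children differently for outcome-related reasons. That covers exercise versus control, and Gince Zumba versus Square Stepping. The text of the choice is certain; the size and direction of any effect on the results are not.

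On the assumed inputs, the type I error of the group-by-time test ranges from about 5% to about 14%, depending mainly on how far removal differs between exercise and control. Every sample size, removal rate, correlation and reliability behind that range is an assumption. If nobody was removed or lost, the per-protocol and as-randomised analyses coincide and no result changes.

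The choice should be fixed. It becomes a must-fix only if any child was removed or lost after randomisation.

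**What to change.** - Keep the section 2.8 sentence as the record of what was done.
- Make the main between-group analysis one of all randomised children in their assigned group, whatever their attendance, using every post-test obtained. Label it post hoc if the data have already been analysed.
- Keep per-protocol as supportive, and label the existing between-group statements in Results as per-protocol until the new analysis has been run.
- Report by arm the numbers randomised, removed (with reasons), without a post-test, and analysed.
- For children without a post-test, use a likelihood-based model or multiple imputation that includes the pre-randomisation baseline. State that this assumes missing at random and does not cure removal related to change.

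**Cost.** A little more analysis work, and the estimates may move in either direction. The gain depends on whether removed children were post-tested, which the protocol does not show. In the reliability model above, a post-test on every randomised child gave bias of 0.00 under all three drivers. Without those post-tests, the likelihood model took baseline-driven bias from between −0.06 and −0.11 to 0.00. It reduced change-driven bias only from 0.17–0.25 to 0.14–0.23. It introduced 0.05–0.09 where removal followed the stable level and per-protocol had none.

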2.5 Outcome Measures

Assessments were conducted at baseline and after the 8-week intervention period.

Primary outcome measures included:

- Cognitive functions assessed using standardized neuropsychological tests (e.g., Stroop Test, Visual-Auditory Digit Span Test)

Secondary outcome measures included:

- Motor performance assessments (Blaze Pod Reaction Time Test)
- Behavioral symptoms evaluated using parent-reported questionnaires (Conners Parent Rating Scale)

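### The primary group × time ANOVA is an unadjusted, per-protocol change-score comparison; adjusting the post-test for baseline in all randomised children who have one would be more precise and would guard against one form of dropout bias

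*Protocol*

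**What the plan says.** Protocol section 2.1 describes a "randomized controlled experimental trial with three parallel groups". Section 2.5 gives two time points: "Assessments were conducted at baseline and after the 8-week intervention period". Section 2.6 adds that "Baseline assessments were conducted prior to randomization", so each randomised child should have a baseline value.

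Section 2.8 opens its analysis with "A per-protocol analysis approach was used" and continues that "pre-test and post-test measurements were analyzed for all three groups". For the primary outcomes it names "a two-factor repeated measures analysis of variance", group by time, with Bonferroni correction. It does not define the per-protocol set. The document gives no number randomised, withdrawn or without a post-test, and no pre-post correlation. Its results section already reports findings in words.

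**The concern.** The model is a stated choice, not a detail left open. A repeated measures ANOVA on a pre/post pair needs both values, and its group × time term tests whether mean change differs between groups. It therefore uses the baseline by subtraction rather than by adjustment.

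Subtraction carries over the measurement noise in the baseline, so the treatment contrast is noisier than it need be. It also leaves the contrast open to regression to the mean. If children with low baselines stop attending in one arm only, the remaining children in that arm start higher and tend to change less, whatever the exercise does. Unequal dropout is plausible: section 2.4 asks for 8 × 2 = 16 sessions in each exercise arm and none in the control arm.

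The per-protocol restriction acts before any model is fitted. It can remove children who do have a post-test but did not adhere, and changing the model alone does not bring them back.

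**Working it through.** The protocol states no sample size, SD, power or dropout figure, so there is none of its own to reproduce. Everything below rests on assumed inputs.

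**1. What the test is.** With two time points, the group × time contrast between an exercise arm and control is (mean post − mean pre) in one arm minus the same in the other, over complete pairs.

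**2. Precision.** Assume equal SD σ before and after, and pre-post correlation ρ.

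- Variance of a change score: 2σ²(1 − ρ).
- Residual variance of the post-test given baseline: σ²(1 − ρ²).
- Ratio, adjusted to change score: (1 − ρ²) / [2(1 − ρ)] = (1 + ρ)/2.
- ρ = 0.5 gives 0.75; ρ = 0.7 gives 0.85.

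A simulation agrees: 20,000 runs, one exercise arm against control, true effect 0.5 SD, 20% of post-tests missing completely at random. At 30 per arm and ρ = 0.5 the SD of the estimate was 0.288 for the change score and 0.253 for ANCOVA, so (0.253/0.288)² = 0.77. At ρ = 0.7 it was 0.223 and 0.210, so (0.210/0.223)² = 0.89. Both lie a little above theory, as expected when the slope is estimated from few children.

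**3. Bias of the change score when dropout depends on baseline in the exercise arms only.** Assume no true effect, a proportion p lost in the exercise arms and none in control, and loss decided by a threshold on a latent variable correlated r with baseline. Among completers the mean baseline shifts by r·φ(z)/(1 − p), where z is the normal quantile for p and φ the normal density. The post-test shifts by ρ times that. The size of the bias in mean change is therefore

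(1 − ρ) · r · φ(z)/(1 − p).

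| ρ | p | r | φ(z)/(1 − p) | Bias (SD) |
|---|---|---|---|---|
| 0.7 | 10% | 0.3 | 0.195 | 0.3 × 0.3 × 0.195 = 0.018 |
| 0.5 | 20% | 0.5 | 0.350 | 0.5 × 0.5 × 0.350 = 0.09 |
| 0.5 | 30% | 0.8 | 0.497 | 0.5 × 0.8 × 0.497 = 0.20 |

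On a scale where higher is better, loss of low-baseline children from the exercise arms biases against exercise; loss of high-baseline children does the reverse.

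**4. Other patterns of missingness.** The same simulation, with 15 or 30 per arm, ρ of 0.5 or 0.7 and about 20 to 24% missing, gave these biases in SD:

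| Missing post-tests | Change score | Baseline-adjusted |
|---|---|---|
| Completely at random | about 0 | about 0 |
| Depend on baseline, same in both arms | about 0 | about 0 |
| Depend on baseline, one arm only | −0.06 to −0.11 | about 0 |
| Depend on the unseen post-test, one arm only | +0.06 to +0.10 | +0.11 to +0.16 |

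**5. What baseline-only children add.** When only post-tests can be missing, the likelihood splits into a part for baseline and a part for post-test given baseline. In a mixed model with a common baseline mean, the treatment contrast lies wholly in the second part, so its point estimate is that of ANCOVA on children with a post-test. With free baseline means, adding the baseline-only children cut the SD only from 0.288 to 0.282, about 2% (30 per arm, ρ = 0.5, missing completely at random).

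**The case against.** A reader might infer that a mixed model rescues the deleted children and is therefore less biased at no cost. The documents do not support that, and neither does the arithmetic. Children with only a baseline add almost nothing to the contrast; the gain comes from conditioning on baseline. The bias advantage appears in just one of the four patterns examined, and in the last pattern the adjusted estimate is the more biased. A child leaving because of lack of improvement is as plausible as one leaving because of a low baseline. There is also a cost: reliance on an untestable missing-at-random assumption.

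A reader might also infer that the reported results are biased. Nothing shows this. The number of missing post-tests is not given and may be zero, and the 0.20 SD end of the range needs 30% one-sided dropout at r = 0.8. Rules for missing data may stand in an analysis plan that is not at hand, so their absence here is no fault.

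Finally, outcomes have already been seen, so replacing the primary model is more than an edit of wording.

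All of this stands, and it limits the point to what is claimed here. It does not touch the precision argument, which holds without any dropout, nor the fact that section 2.8 itself fixes both the per-protocol set and the unadjusted model.

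**Conclusion.** The point holds as a worthwhile, inexpensive improvement, not as proof of a biased result. The stated analysis is a per-protocol, complete-pair change-score comparison. Adjusting for a baseline already collected would lower the variance of the contrast by about 25% at ρ = 0.5 or 15% at ρ = 0.7, assuming equal SDs before and after and a common slope. The bias in the working is conditional on missingness that depends on baseline and differs by arm. The per-protocol restriction is a further weakness of unknown size, because the excluded children are neither defined nor counted.

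**What to change.** In section 2.8, make the primary analysis a comparison of post-test scores adjusted for baseline: ANCOVA, or the equivalent mixed model with a common baseline mean. Include every randomised child with a post-test, in the assigned group and regardless of adherence, and keep the same Bonferroni-corrected contrasts between the three groups.

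Alongside it:

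- report the number of missing post-tests by arm;
- state the assumption that post-tests are missing at random given baseline;
- add a sensitivity analysis in which missingness depends on the unseen post-test;
- keep the per-protocol repeated measures ANOVA as a supportive analysis.

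The cost is a rewording of 2.8, a re-run in the SPSS software already named, and recovery of post-tests from any children left out for non-adherence. No new measurement is needed. The change must be disclosed as post hoc, with both sets of results shown.

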2.2 Participants

Children diagnosed with Attention Deficit Hyperactivity Disorder were recruited for the study. Participants were within the age range of **8-12** years and were diagnosed according to DSM criteria by a qualified clinician.

Inclusion criteria included:

- A clinical diagnosis of ADHD
- Being within the specified age range
- Ability to follow verbal instructions
- Ability to read and understand Turkish language
- Being under medication at least 2 months prior to the study

Exclusion criteria included:

- Presence of neurological, orthopedic, or psychiatric disorders other than ADHD
- Participation in regular structured exercise programs during the study period
- Inability to perform any physical activity

Written informed consent was obtained from parents or legal guardians prior to participation.

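### Demographics are used only in baseline significance tests; a pre-chosen age covariate acting on the treatment contrast would be more useful, though the stake is modest

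*Protocol*

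**What the plan says.** Protocol section 2.8 gives demographics one use: a one-way ANOVA and a "chi-square test were used to analyze baseline demographic characteristics of the participants". The threshold is general: "A p-value of less than 0.05 was considered statistically significant". For the primary outcomes, "a two-factor repeated measures analysis of variance (group \times time) with Bonferroni post hoc correction was applied", and "Within-group changes were analyzed using paired-samples t-tests". No covariate is named in either analysis. The analysis set is per-protocol.

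Section 2.6 fixes the timing: "Baseline assessments were conducted prior to randomization". Section 2.3 describes random assignment to three arms without mentioning stratification. Section 2.2 states "Participants were within the age range of 8-12 years" and makes age an eligibility criterion ("Being within the specified age range"), so every child's age has to be known. Section 2.5 sets two assessments, at baseline and after 8 weeks, and the Results text describes the outcomes as changes between them.

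The document gives no arm size, allocation ratio, age SD or list of the demographic variables.

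**The concern.** A baseline test in a randomised trial asks whether chance produced the difference between arms. For all randomised children the answer is known in advance: it did. A small p-value is then a chance finding, and a large one does not show that the arms are alike. What matters for the outcome is the size of the imbalance multiplied by the variable's relation to the quantity analysed, and the p-value measures neither.

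Meanwhile age, which is recorded and could plausibly relate to how much a child matures, benefits from practice or responds over 8 weeks, is absent from the stated outcome model. At stake are some bias in an arm contrast when the arms happen to differ in age, and some precision.

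**Working it through.** The protocol has no figure to reproduce. Everything below is illustration under stated assumptions: 1:1:1 allocation, two-sided 5% level, and age SD of 1.15 years (uniform from 8 to 12, 4/√12) to 1.44 years (uniform from 8 to under 13, 5/√12).

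**1. What the baseline tests can show.** With k independent demographic variables, the chance of at least one p<0.05 under sound randomisation is 1 − 0.95^k: 18.5% for k = 4 and 26.5% for k = 6 (k is assumed).

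If one arm's mean age differs from the other two by d SD, F = n·d²/3, so the smallest gap flagged is √(3·Fcrit/n). For the per-protocol set, where selective exclusion could create a real shift, power comes from the noncentral F distribution.

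| Per arm (assumed) | Smallest gap flagged | Power, 0.5 SD shift | Power, 0.8 SD shift |
|---|---|---|---|
| 15 | 0.80 SD | 26% | 58% |
| 20 | 0.69 SD | 34% | 72% |
| 30 | 0.56 SD | 49% | 89% |
| 40 | 0.48 SD | 62% | 96% |

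At 20 per arm, 0.69 SD is about 0.8 year (0.69 × 1.15) to 1.0 year (0.69 × 1.44). An observed gap of 0.5 SD gives F(2,57) = 20 × 0.25/3 = 1.667, p = 0.198.

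**2. What reaches the treatment contrast.** Let age act on the baseline score with slope b and on the post score with slope b + c. The change then contains c × age, and b drops out. An age gap of d therefore biases the group-by-time contrast by c × d. If c = 0 the bias is zero, however strongly age drives the level of the score.

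A two-arm simulation with no treatment effect shows this (15 per arm, age gap 0.8 SD, age-score correlation 0.5, pre-post correlation about 0.7; bias in SD of the score):

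| c | Bias, change contrast | False-positive rate, change contrast | Bias, ANCOVA on baseline only | Bias, ANCOVA on baseline and age |
|---|---|---|---|---|
| 0 | −0.005 | 4.9% | 0.116 | −0.002 |
| 0.1 | 0.075 | 5.9% | 0.176 | −0.002 |
| 0.2 | 0.155 | 7.7% | 0.235 | −0.002 |

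Here the variance of change not due to age is 2 × (1 − 0.7) = 0.6, so c = 0.1 and 0.2 correspond to age-change correlations of 0.1/√0.61 = 0.13 and 0.2/√0.64 = 0.25.

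**3. Size as a function of the age-change correlation r.** Take 20 per arm and d = 0.5, with the SD of change set to 1. Bias = r·d, SE = √(2/20) = 0.316, and the error rate given this gap is P(|r·d/SE + √(1 − r²)·Z| > 1.96), with Z standard normal. Adjustment removes a share r² of the residual variance.

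| r | Bias (SD of change) | Bias/SE | Error rate given the gap | Variance removed |
|---|---|---|---|---|
| 0.1 | 0.05 | 0.16 | 5.2% | 1% |
| 0.2 | 0.10 | 0.32 | 5.7% | 4% |
| 0.3 | 0.15 | 0.47 | 6.5% | 9% |
| 0.5 | 0.25 | 0.79 | 8.9% | 25% |

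The last row is an upper illustration; nothing in the document supports so strong a link between age and change.

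**4. How often such a gap arises.** A given pair of arms differs by 0.5 SD or more with probability 2 × (1 − Φ(0.5/0.316)), about 11% at 20 per arm; with SE = √(2/30) it is about 5% at 30.

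**The case against.** The strongest reply is that the planned contrast already deals with most of the problem. A reader might infer that a chance age imbalance stays uncorrected in every outcome contrast. The documents do not support that: group by time over two visits compares changes, and a stable age effect cancels. This objection stands and limits the point to age effects on change.

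A reader might also infer that the test is invalid. It is not. Chance imbalance is part of the nominal 5%, and averaged over randomisation the unadjusted contrast keeps that rate. The raised rates above apply only to draws in which the gap occurred. The per-protocol set weakens this protection, because the arms analysed need not be the arms randomised. For the same reason, a true null by design can be claimed only for all randomised children.

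Third, the protocol nowhere says that a non-significant baseline test will be read as equality of the arms, or that the tests decide on adjustment. That misuse is an inference and is not charged here. Nor can one say that a large age gap would go unnoticed: at 40 per arm a 0.8 SD shift is flagged 96% of the time.

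Finally, covariates are often left to a statistical analysis plan, and none is shown. The point therefore rests on what section 2.8 affirmatively states, namely the baseline tests and a model without covariates. It does not rest on the absence of an adjustment plan elsewhere.

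**Conclusion.** The point holds at low severity. The stated baseline tests answer no useful question among all randomised children and are a weak check in the per-protocol set. The stated model leaves unused a variable the trial must already hold.

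The cost is bias conditional on an age imbalance, plus some lost precision. It is close to nil at an age-change correlation of 0.1 and modest at 0.2 to 0.3. It depends on arm size, age SD and that correlation, all assumed here. Removing the baseline tests by itself changes no treatment result; the gain comes from the age term.

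**What to change.** In section 2.8, replace the baseline ANOVA and chi-square tests with descriptive summaries by arm for all randomised children. Include age, as a continuous covariate, in the analysis of every outcome whatever the observed imbalance, in a form that acts on the treatment contrast. Either of these will do:

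- an explicit age-by-time term in the repeated-measures model; or
- an ANCOVA of the post score on group, baseline score and age.

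An age main effect alone is not enough. With two complete visits it leaves the group-by-time estimate unchanged. If ANCOVA is chosen, age should go in together with the baseline score: in the simulation, baseline score alone left a bias of 0.12 SD even when age acted equally at both visits.

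The document already reports results, so if these are known the age-adjusted analysis cannot be presented as chosen in advance and should be labelled a sensitivity analysis.

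The cost is a few sentences and one or two degrees of freedom, with no new data. If age is unrelated to change, the planned change contrast gains nothing from the age term.

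### Section 2.8 names a between-group test for the primary outcomes only, yet the Results report significance against control on both secondary outcomes

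*Protocol*

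**What the plan says.** Protocol section 2.8 names four procedures and gives each a purpose.

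- One-way ANOVA and Pearson's chi-square "were used to analyze baseline demographic characteristics of the participants".
- The group by time ANOVA with Bonferroni post hoc correction is introduced by "To examine the primary outcome variables, a two-factor repeated measures analysis of variance".
- Paired t-tests serve change within an arm: "Within-group changes were analyzed using paired-samples t-tests". That sentence names no outcome.

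The section also says in general terms that "pre-test and post-test measurements were analyzed for all three groups".

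Section 2.5 makes the cognitive tests primary. It lists two secondary outcomes: "Motor performance assessments (Blaze Pod Reaction Time Test)" and "Behavioral symptoms evaluated using parent-reported questionnaires (Conners Parent Rating Scale)".

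Section 4, Results, under Motor Performance, states "Changes in reaction time from baseline to post-intervention were analyzed" without naming a test, and then that "both intervention groups exhibited significant improvements in motor performance relative to the control group". It adds that the gain was larger in the Square Stepping group (SSEG) than in the Gince Zumba group (GZG). Under Behavioral Symptoms it reports significant reductions in both exercise groups, against control and also against baseline. No test, estimate or p-value accompanies any of these statements.

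**The concern.** A claim of significance against control needs a test that uses data from both arms. For the two secondary outcomes section 2.8 names none. A reader therefore cannot tell whether the claims rest on a contrast of change between arms, or on the exercise arms each passing a paired test while control did not.

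The second route is a known error. Section 2.6 says the same tools were used before and after, 8 weeks apart, so every arm may improve through practice or maturation. A paired test counts such a shared gain as change; a group by time test removes it. The motor and behavioural statements are also the only ones in the Results that are called significant against control.

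**Working it through.** **Step 1. Match tests to outcomes.**

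| Outcome (section 2.5) | Between-group test in 2.8 | Within-group test in 2.8 | Claim against control in Results |
|---|---|---|---|
| Cognitive tests (primary) | Group by time ANOVA, Bonferroni | Paired t-test | Improvement stated, no contrast with control |
| BlazePod (secondary) | None named | Paired t-test | Significant, both exercise arms |
| Conners (secondary) | None named | Paired t-test | Significant, both exercise arms |

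One-way ANOVA and chi-square do compare groups, but only on baseline demographics. The two outcomes with a claim of significance against control are thus the two without a named between-group test.

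**Step 2. What a paired test can support.** It tests whether mean change within one arm is zero. It can support the Conners statement about change from baseline. It cannot support a statement about the difference in change between two arms.

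**Step 3. Illustration of the stake.** The protocol gives no sample size, variance, correlation or test statistic, so there is no figure of its own to reproduce, and every input below is assumed: no treatment effect; the same retest gain g (in SD units) in all arms; n = 15, 20 or 30 per arm; pre-post correlation r = 0.5 to 0.8; normal changes; two-sided 5% tests.

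- Standardised change: dz = g / √(2(1 − r)).
- Noncentrality: dz × √n, with n − 1 degrees of freedom.
- u = P(significant improvement) and l = P(significant worsening) in one arm.
- P(both exercise arms significantly improved, control not significant) = u²(1 − u − l).

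Example with g = 0.2, r = 0.7, n = 20: dz = 0.2/√0.6 = 0.258; noncentrality 0.258 × √20 = 1.155; u = 0.194, l = 0.001; result 0.194² × 0.805 = 0.030.

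| r = 0.7 | n = 15 | n = 20 | n = 30 |
|---|---|---|---|
| g = 0.2 | 0.020 | 0.030 | 0.055 |
| g = 0.3 | 0.059 | 0.088 | 0.133 |

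Over all r from 0.5 to 0.8 and g of 0.2 or 0.3:

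- Minimum: 0.010 (r = 0.5, g = 0.2, n = 15).
- Maximum: 0.146 (r = 0.8, g = 0.3, n = 30).

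Smaller gains give much smaller figures:

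- g = 0.1: 0.003 to 0.015.
- g = 0.05: 0.001 to 0.004.
- No gain: 0.025² × 0.95 = 0.0006.

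**Step 4. Comparator.** Contrasts of change with pooled variance, each at 0.05/3 = 0.0167, were simulated under the same assumptions with 400,000 trials per setting. Both exercise arms came out significantly better than control with probability 0.0010 to 0.0012, whatever the shared gain.

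**The case against.** The strongest reply is that the same ANOVA was run on all outcomes and section 2.8 is merely worded narrowly. The general sentence about analysing all three groups carries no limit to primary outcomes. The Conners statement separates the comparison with control from the comparison with baseline, which fits a between-group contrast plus a paired test. Nor does the section say that the ANOVA was used only for primary outcomes. This stands as a real possibility. A reader might infer from the mismatch that the secondary results are wrong or came from paired tests alone; the document supports neither inference.

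A second reply is that a protocol commonly leaves secondary models to the SAP. Silence alone would indeed be no finding. Here, however, the same document assigns its between-group test to the primary outcomes and then reports significance against control on the others. A separate SAP could name the test, but it would not make this document's methods and results agree.

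Third, the ranking of the exercise arms on reaction time is not called significant and can be read as a description of mean changes. That is right: it needs a label, and need not be withdrawn outright.

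Fourth, the probabilities rest wholly on assumed inputs, and one assumed gain is applied alike to a reaction-time task and a parent questionnaire. That is also right. They show the kind of error at stake and should not set its weight.

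**Conclusion.** The point holds as a mismatch between stated methods and reported conclusions, and it should be fixed. Confidence is high on the wording and does not extend to any analytic error. As written, section 2.8 offers only one-arm tests for BlazePod and Conners, and these cannot support significance against control.

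The range of 0.010 to 0.146 depends on the assumed sample size, correlation and retest gain. It applies only if paired tests alone were used. It does not apply to the primary outcome, which has a suitable model, nor to the secondary outcomes if a between-group test was run.

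**What to change.** 1. In section 2.8, extend the stated group by time model to BlazePod and Conners, with Bonferroni-corrected contrasts of change across the three arm pairs. If such a test was already run, name it there.
2. Base the statements of benefit over control on those contrasts, and treat paired t-tests as descriptive. If no between-group result is available, withdraw the claim of significance against control for both outcomes.
3. Label the reaction-time ranking as descriptive unless the GZG-SSEG contrast supports it.

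The cost is small: one sentence if the test was run, otherwise an already stated model applied to two outcomes already collected. The downside is that some claims against control, or the ranking, may not survive.
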